### Dose Interruptions

An interruption is defined as an IV medication which is not administered (i.e. 0 dose) on one or more planned dosing days. Interruptions are identified on the [Study Drug] Administration eCRF pages (e.g. “Has the subject received a dose of Oxaliplatin during this visit?”). Please note that dose interruptions, as defined here, are not the same as drug interruptions captured on the Treatment Administration Modification Details eCRF page. The number and percentage of patients with dose

---

interruptions, the corresponding reasons, the number of interruptions observed, and the length of interruption will be summarized. Length of dose interruptions is measured in cycles.

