5.1.2.2.2 Chemotherapy Arm

Subjects randomly assigned to the maintenance chemotherapy arm will receive first-line chemotherapy according to the dosing schedule (see Section 6.2 and Table 3 to Table 4) or in accordance to the label instructions and per local guidelines) until disease progression, unacceptable toxicity, for the accepted maximal duration of the agent(s) selected, or any of the criteria for withdrawal from trial treatment is fulfilled (Section 5.5).

The dose and schedule during the Maintenance Phase are as follows:

Subjects randomly assigned to chemotherapy will continue the same regimen of oxaliplatin-fluoropyrimidine doublet as they received during the Induction Phase until disease progression.

- Subjects who are not deemed eligible to receive further chemotherapy will receive BSC alone with no active therapy. Prior to randomization, Investigators must specify BSC treatment for these subjects (see Table 5)
- For subjects receiving chemotherapy (oxaliplatin + 5-FU or oxaliplatin + capecitabine), dose modifications after the starting dose are allowed if the continuation of the oxaliplatin-fluoropyrimidine doublet, or a component thereof, is prohibited by toxicity. For subjects intolerant to further oxaliplatin, single-agent capecitabine or 5-FU + leucovorin will be an option for dose modification.

Additionally, in order to reduce the incidence and severity of nausea and vomiting as well as the severity of hypersensitivity reactions, subjects will be administered pretreatment prior to each therapy infusion per local institutional practice.

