### Treatment Duration

For subjects on Avelumab arm, the duration of treatment (weeks) during the study is defined as:

$$\text{Treatment duration (weeks)} = (\text{last dose date} - \text{first dose date} + 14) / 7$$

For subjects on chemotherapy arm (oxaliplatin + 5-FU or oxaliplatin + capecitabine), the duration of treatment (weeks) is defined as follows for both the Induction Phase and the Maintenance Phase, while the first dose and last dose date are relatively to the first and last dose date in the Induction and Maintenance Phase, respectively.

- Oxaliplatin + 5-FU arm:
  - Treatment duration for oxaliplatin (weeks) = (last dose date – first dose date + 14) / 7
  - Treatment duration for 5-FU (weeks) = (last dose date – first dose date + 14) / 7
- Oxaliplatin + capecitabine arm:
  - Treatment duration for oxaliplatin (weeks) = (last dose date – first dose date + 21) / 7Since capecitabine is taken as a tablet twice daily for 2 weeks followed by a 1-week rest period once every 3 weeks, treatment duration is calculated as follows:
  - Treatment duration of capecitabine (weeks) = (last dose date – first dose date + 7) / 7

Duration of Regimen is defined for subjects who receive both oxaliplatin and 5-FU or capecitabine. For these subjects, Duration of Regimen is equivalent to the treatment duration of whichever chemotherapy is discontinued first. For example, if a subject receives oxaliplatin and 5-

---

FU and discontinues oxaliplatin before discontinuing 5-FU, Duration of Regimen will be equal to the treatment duration for oxaliplatin. In the case a subject discontinues oxaliplatin and capecitabine on the same day (and the subject does not receive further capecitabine doses) the treatment duration for oxaliplatin will be selected as the Duration of Regimen for this subject.

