### **Relative Dose Intensity**

The relative dose intensity (RDI) is defined as the actual dose intensity divided by the planned dose per cycle and expressed in %.

The summary of treatment exposure and compliance will be calculated for both Induction Phase and Maintenance Phase, and will include the following information:

- Duration of therapy (weeks)
- Total number of infusions received (avelumab and IV chemotherapy)
- Total number of Capecitabine doses received

The following will be included, broken down by separate chemotherapy treatment in the chemotherapy arm:

- Cumulative dose of therapy (mg/kg or mg/m^2)
  - Dose intensity (mg/kg/cycle) or (mg/m^2/cycle)
-

- Relative dose intensity of therapy categories: < 80%, 80% - < 90%, 90% - < 110%, >= 110%

A listing of treatment exposure and compliance will also be created to summarize the information listed above for each subject.

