### Dose Reductions

Dose reduction will be calculated for the chemotherapy arm only in the Maintenance Phase. Per study protocol, there will be no dose reductions for the avelumab treatment arm. A dose reduction is defined as an actual non-zero cumulative dose < 90% of the planned cumulative dose for a given treatment cycle. For subjects receiving Capecitabine or 5-FU as a push followed by a drip, any skipped doses within the cycle will be counted as part of the planned cumulative dose for the cycle (i.e. will contribute to the denominator of the calculation). Dose reductions are counted on a per-cycle basis and do not consider whether previous doses were reduced. The number of subjects with at least one dose reduction as well as a categorical breakdown of dose reductions (1 / 2 / 3 / >=4) will be summarized for the chemotherapy/BSC arm.

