### Dose Delays

Dose delays will be calculated for Maintenance Phase IV study drugs only. Delays are defined as infusions given  $\geq 3$  days from the planned administration date and will be derived based on study drug administration date and will be grouped into the following categories based on the deviation of the actual to the planned treatment administration day (relative to the previous treatment administration date):

- No delay (including 1-2 days delays)
- 3-6 days delay
- 7 or more days delay

For example, if a subject receives avelumab on Day 1, then the next avelumab administration date should be on Day 15; however, if the subject receives avelumab on Day 16 or 17, this is considered as a “No delay”.

Number and percentage of subjects with delayed study drug administration and maximum length of delay, i.e. the worst case of delay if subjects have multiple dose delays will be summarized by treatment group.

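### A Maintenance cycle with no capecitabine at all meets none of the SAP's dose-modification definitions, so it goes uncounted unless oxaliplatin is also withheld or delayed

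*SAP*

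**What the plan says.** SAP Section 14 sets three rules for dose modifications in the Maintenance Phase.

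- **Reductions** (chemotherapy arm only): "A dose reduction is defined as an actual non-zero cumulative dose < 90% of the planned cumulative dose for a given treatment cycle". For capecitabine, "any skipped doses within the cycle will be counted as part of the planned cumulative dose for the cycle", so missed tablets lower the ratio.
- **Delays**: "Dose delays will be calculated for Maintenance Phase IV study drugs only".
- **Interruptions**: "An interruption is defined as an IV medication which is not administered (i.e. 0 dose) on one or more planned dosing days". The number and percentage of subjects, reasons, number of interruptions and length in cycles are summarized.

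The same section describes capecitabine as a tablet taken twice daily for two weeks of each three-week cycle. Protocol Section 5.1.2.2.2 allows a control regimen with no IV drug: "For subjects intolerant to further oxaliplatin, single-agent capecitabine or 5-FU + leucovorin will be an option for dose modification".

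**The concern.** Each rule excludes the zero-dose oral cycle for a different reason: the reduction rule because the dose is zero, the other two because the drug is not IV. The count therefore rises with the amount of capecitabine missed and falls to nothing when all of it is missed.

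The gap also runs one way. A missed avelumab, oxaliplatin or 5-FU infusion is always eligible to be an interruption; a withheld capecitabine cycle never is. Safety and tolerability are a stated secondary objective, and interruption counts are part of how the two arms' treatment delivery will be described. Subjects who moved to single-agent capecitabine because they could not tolerate oxaliplatin can have neither a delay nor an interruption recorded while on that regimen.

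**Working it through.** The plan gives no figure for this point, so the rules are applied directly.

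**Step 1: the reduction rule.** The planned cycle dose is 1000 mg/m² × 2 per day × 14 days = 28,000 mg/m². Assume the remaining doses are taken in full.

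| Days skipped | Dose taken (mg/m²) | % of plan | Counted as reduction? |
|---|---|---|---|
| 1 | 26,000 | 92.9 | No (not below 90%) |
| 2 | 24,000 | 85.7 | Yes |
| 7 | 14,000 | 50.0 | Yes |
| 13 | 2,000 | 7.1 | Yes |
| 14 | 0 | 0.0 | No (zero dose) |

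In single doses, the smallest omission that counts is 3 of 28 (25/28 = 89.3%).

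**Step 2: which zero-dose cycles are lost.** Oxaliplatin is due on Day 1 of the same three-week cycle.

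| What happens to oxaliplatin | Is the subject counted? |
|---|---|
| Also withheld | Yes, as an oxaliplatin interruption |
| Given at least 3 days late | Yes, as an oxaliplatin delay |
| Given on schedule | No |
| Permanently stopped (single-agent capecitabine) | No; no IV drug is planned |

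**Step 3: whether relative dose intensity (RDI) recovers the omission.** The SAP gives "Treatment duration of capecitabine (weeks) = (last dose date – first dose date + 7) / 7". Dose intensity is cumulative dose ÷ (weeks ÷ 3), and RDI divides that by the planned cycle dose. For four planned cycles at full dose:

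- None omitted: first dose day 1, last dose day 77. Duration is (77 − 1 + 7)/7 = 11.857 weeks, or 3.952 cycles. RDI = 4/3.952 = 101.2%.
- One middle cycle omitted: same duration, three cycles' dose. RDI = 3/3.952 = 75.9%.
- First or last cycle omitted: duration is (56 − 1 + 7)/7 = 8.857 weeks (the same span when the first is omitted), or 2.952 cycles. RDI = 3/2.952 = 101.6%.

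RDI thus shows a middle omission but not one at either end, because duration runs only from the first to the last dose actually taken.

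**Step 4: scale, on assumption only.** Let q be the per-cycle chance that a subject on capecitabine has a zero-dose cycle not already counted through oxaliplatin, with cycles independent. Over four cycles the share with at least one uncounted omission is 1 − (1 − q)⁴: 7.8% for q = 2%, 18.5% for q = 5% and 34.4% for q = 10%. The documents support no particular q, and the denominator is capecitabine subjects, not the control arm.

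**The case against.** **The IV limit was deliberate.** The SAP 4.1 log for version 3.0 records a clarification that interruptions concern IV medications, and Protocol Section 8.5.6 promises neither interruption nor reduction counts. This stands as an explanation: no protocol commitment is broken. But it supplies no rule for the oral drug, and the reduction rule shows that the SAP means to capture missed capecitabine.

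**Other outputs show it.** SAP 14 tabulates "Total number of Capecitabine doses received", cumulative dose and RDI, and lists drug administration; SAP 11.1 tabulates discontinuation by drug, including capecitabine. This stands in part. Dose totals cannot separate a withheld cycle from a shorter course, and RDI misses the first and last cycles. The listing of modifications with reasons covers reductions, delays and infusion rate reductions only. Deviation INVPRO12 in Appendix I covers missed chemotherapy only where the cause is not an adverse event, which leaves out toxicity-driven omissions.

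**Most omissions may be counted anyway.** This stands as a real limit. A reader might infer that every omitted capecitabine cycle is lost, and might multiply an assumed 40–70% capecitabine share by an assumed 10–25% omission rate to put 4–18% of control subjects outside every table. The documents support neither rate, and the product includes cycles already counted through oxaliplatin.

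**The arms are barely compared on this.** Reductions are tabulated for chemotherapy only, so there is no avelumab count to set against them. This stands: the between-arm effect is confined to interruptions.

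**Conclusion.** The definitional gap is certain from the SAP text. It concerns one drug in one control regimen, and only zero-dose cycles in which oxaliplatin is given on schedule or is no longer part of treatment. For single-agent capecitabine every withheld cycle is missed.

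The direction is understatement, in the capecitabine modification counts and in the control-arm interruption counts that stand beside avelumab's. The amount cannot be derived from the documents.

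A reader might go further and conclude that control chemotherapy will generally look better tolerated than it was. The documents do not support that: adverse event tables, serious events and events leading to discontinuation do not use these definitions. Nor are overall survival, alpha or power touched. This is a correctable error in a descriptive exposure summary.

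**What to change.** Add to SAP 14, Dose Interruptions: *For capecitabine, an interruption is a Maintenance cycle with zero cumulative capecitabine dose that occurs before permanent discontinuation of capecitabine.* Report the number and the length in cycles alongside the IV drugs, and the reason where the eCRF collects it. Keep the rule of a non-zero dose below 90% for partial omission.

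The end point must be discontinuation of capecitabine itself, not of study treatment. The SAP allows the components of a regimen to be stopped separately, so a subject who stops capecitabine for good and continues oxaliplatin would otherwise log a new interruption every cycle.

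The cost is one sentence and minor programming, since the reduction rule already needs capecitabine dose per cycle. Control-arm interruption counts will rise. Whether reasons for zero-dose capecitabine cycles are collected is not shown in the documents and should be checked first. No clinical rule changes.

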### Infusion Rate Reductions

Infusion rate reduction will be calculated for the Avelumab treatment arm in the Maintenance Phase only. Infusion rate reductions will be derived based on the infusion rate recorded by visit on the eCRF. Number of subjects with at least one infusion rate reduction as well as a breakdown of the number of infusion rate reductions (1 / 2 /  $\geq 3$ ) will be summarized.

A listing of study drug administration will be created with the information collected on the applicable treatment administration details eCRF pages.

Subjects with dose reductions, dose delays or infusion rate reductions and the corresponding reasons will be summarized in a listing.

## 15 Endpoint Evaluation

[figure not shown]
A hierarchical test strategy will be used to control the overall type I error rate for the primary endpoint of OS, between analyses in all randomized subjects, and PD-L1+ subjects and key secondary endpoints of PFS and BOR in all randomized subjects in the following hierarchical order:

- 1: H01: OS in the FAS Analysis Set and H02: PD-L1+ Analysis Set in the Maintenance Phase
- 2: H03: PFS in the FAS Analysis Set in the Maintenance Phase
- 3: H04: BOR in the FAS Analysis Set in the Maintenance Phase

The overall 2.5% (1-sided) type I error will be split between OS in all randomized subjects and PD-L1+ subjects with 2.0% (1-sided) and 0.5% (1-sided), respectively. One interim analysis is planned for OS in all randomized subjects. A Lan-DeMets alpha spending function for O'Brien-Fleming boundaries will be used to control the overall type I error rate of OS in all randomized subjects at 2% between the interim and primary analysis (see Section 7.2).

For the primary endpoint, a closed testing procedure with weighted Bonferroni tests, described by Hommel et al. (2), as illustrated in Figure 1, will be used for determining significance of the dual hypothesis primary testing at the primary analysis.

Figure 1 Testing strategy

At the primary analysis, if any of the two null hypotheses of OS (evaluated in all randomized subjects and in PD-L1+ subjects) is rejected, the corresponding alpha level will be recycled between both populations. The alpha recycling approach is as follows:

1. If the null hypothesis of OS in all randomized subjects is rejected at the primary analysis, the 2% (1-sided) alpha allocated to OS in all randomized subjects will be recycled to OS in PD-L1+ subjects, then 2.5% (1-sided) alpha level will be used for OS in PD-L1+ subjects.
2. If the null hypothesis of OS in PD-L1+ subjects is rejected, the 0.5% alpha allocated to OS in PD-L1+ subjects will be recycled to OS in all randomized subjects. In this case, the alpha for OS in all randomized subjects is 2.5% (1-sided) and the 1-sided boundary at the primary analysis would be recalculated by keeping the alpha level used at interim analysis unchanged. Thus, assuming the planned number of events are observed at each analysis, the 1-sided boundaries would then be 0.0072 at the interim analysis and 0.0233 at the primary analysis.

Table 3 summarizes the operating characteristics and efficacy boundaries, in the event that planned number of events are observed for OS in all randomized subjects at both the interim and primary analyses.

**Table 3**                      **Planned Efficacy Boundaries of OS in all randomized subjects and in PD-L1+ subjects**

Look	Hypothesis Test	Info Fraction	Approx. Cum. Events of OS	Cumulative Type I Error (1-sided)	Efficacy Boundaries	
					Z-scale	p-scale (1-sided)
Interim	OS in all randomized subjects	~75%	267	0.0072	2.45	0.0072
Primary	OS in all randomized subjects (if the test for OS in PD-L1+ subjects is not significant)	100%	356	0.0200	2.10	0.0178
	OS in all randomized subjects (if the test for OS in PD-L1+ subjects is significant)	100%	356	0.0250	1.989	0.0233
	OS in PD-L1+ subjects (if the test for OS in all randomized subjects is not significant)	100%	112	0.0050	2.576	0.0050
	OS in PD-L1+ subjects (if the test for OS in all randomized subjects is significant)	100%	112	0.0250	1.960	0.0250

PFS, followed by BOR, will be tested if and only if both null hypotheses for OS in all randomized subjects and PD-L1+ subjects are rejected at the primary analysis. In that case, PFS will be tested with full 2.5% (1-sided) type I error at the primary analysis. BOR will be tested with full 2.5% (1-sided) type I error at the primary analysis if and only if the null hypothesis of PFS is rejected. All analyses including OS in PD-L1+ subjects, CCI [REDACTED]

No formal adjustment for multiplicity will be undertaken for non-key secondary endpoints, sensitivity analyses, or CCI [REDACTED] analyses.

Statistical analyses will be performed using SAS® version 9.4 or higher.

### 15.1 Primary Endpoint Analyses

*Analysis sets: FAS, PD-L1+, PP*

The primary endpoint for maintenance therapy is OS. The primary analysis sets will be the FAS Analysis set and PD-L1+ Analysis Set. The following analysis will be conducted in the same manner

for both FAS and PD-L1+ Analysis sets. For OS, the difference between the two treatment arms will be compared using a stratified, 1-sided, log-rank test. The stratification factor will be region (Asia versus non-Asia). Control of type I error and statistical significance is discussed above (Section 5). The following null hypothesis will be tested:

$$H_0: \lambda_A(t) / \lambda_B(t) \geq 1, \text{ versus } H_1: \lambda_A(t) / \lambda_B(t) < 1$$

where  $\lambda(t)$  represents the hazard rate (corresponding to each endpoint) at time  $t$  for treatment arms A (avelumab) and B (chemotherapy/BSC).

### 15.1.1 Primary Efficacy Analysis of Overall Survival

*Analysis sets: FAS, PD-L1+, PP*

The primary efficacy analysis of OS in all randomized subjects and in PD-L1+ subjects will be performed on the FAS and PD-L1+ analysis sets, respectively. All data required for the calculation of time to event will be taken from the eCRF.

OS is defined as the time from randomization to the date of death, regardless of the actual cause of the subject's death. For subjects who are still alive at the time of data analysis or who are lost to follow-up, OS time will be censored at the last recorded date that the subject is known to be alive (i.e. the date of last contact, as defined in Section 10) as of the data cut-off date for the analysis.

$$\text{OS (months)} = (\text{Date of death or censoring} - \text{Date of randomization} + 1) / 30.4375$$

For the endpoint of OS, the alpha level used for all randomized subjects and PD-L1+ subjects will be determined as specified in Sections 6, 7.27.1, 5, based on the number of events observed at the time of analysis and the significance of the test in each of the two populations.

The treatment effect will be estimated using a Cox Proportional Hazard model stratified by the randomization strata to calculate the hazard ratio. Each stratum will define a separate baseline hazard function (using the 'STRATA' statement in SAS PROC PHREG), i.e. for the  $i$ -th stratum the hazard function is expressed as:  $h(i; t) = h(i, 0; t) \exp(x\beta)$ , where  $h(i, 0; t)$  defines the baseline hazard function for the  $i$ -th stratum and  $x$  defines the treatment group (0= chemotherapy/ BSC, 1= avelumab) and  $\beta$  is the unknown regression parameter. The hazard ratio of avelumab versus chemotherapy/ BSC (with chemotherapy/ BSC as reference), together with the corresponding Wald two-sided 95% confidence intervals (CIs), will be presented.

Ties will be handled by replacing the proportional hazards model by the discrete logistic model (Ties=Discrete option in SAS PROC PHREG).

Kaplan-Meier estimates (product-limit estimates) will be presented by treatment group together with a summary of associated statistics including the median survival time with two-sided 95% CIs. In particular, the survival rate at 3, 6, 9, 12, 15, 18, 21, and 24 months will be estimated with

---

corresponding two-sided 95% CIs. Survival rate for additional months may be displayed, in the event that such a value is estimable at months 27 and beyond. The CIs for the median will be calculated according to [Brookmeyer and Crowley \(3\)](#) and the CIs for the survival function estimates at the time points defined above will be derived using the log-log transformation according to [Kalbfleisch and Prentice \(7\)](#) (conftype=loglog default option in SAS Proc LIFETEST). The estimate of the standard error will be computed using Greenwood's formula.

Frequency (number and percentage) of subjects with an event (death) and censoring reasons will be presented by treatment arm. Censoring reasons are as follows:

- Alive
- Withdrawal of consent
- Lost to follow-up

Lost to follow-up will include the following subjects:

- Lost to follow-up status is collected on the eCRF page prior to the analysis cut-off;
- Subjects with the last contact date > 14 weeks prior to the analysis cut-off date (duration of 14 weeks is based on the assessment schedule of every 12 week for survival follow-up interval + 2-week window)

The OS time or censoring time and the reasons for censoring will also be presented in a subject listing.

### 15.1.2 Sensitivity Analyses and Model Checks

*Analysis sets: FAS, PD-L1+*

